5.1 Timing of analyses

The last subject to be randomized was entered into the trial July 19, 2021, meaning all subjects will have at least 3 years of follow-up on August 9, 2024, allowing for the visit window of 21 days. Analyses of the primary endpoint, and of secondary endpoints 1-3 and 6 will be performed as soon as possible after August 9, 2024. All sites need to be closed by KTA before any analyses can be performed, see Section 4.10 for details.

The analysis of secondary endpoints 4 and 5 (OS assessed at 5 years from randomization) will be possible from August 19, 2026, allowing for the 30-day visit window of Visit 16. Vital status and death date (if any) for subjects having reached EoS before visit 15 will have to be collected from sites before the analyses of secondary endpoints 4 and 5 can be conducted.

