6.2 Derived variables

6.2.1 Endpoint variables

For the primary endpoint TTR assessed at 3 years, subjects will be censored at the date for which they are last known to be free of CRC recurrence. Subjects who are alive and free of CRC recurrence at 3 years plus 21 days (allowing for the 21-day visit-window) will be censored at that time-point. Subjects who have withdrawn their written informed consent during the trial will be censored at the withdrawal date. Subjects who have relocated, and where information on endpoints is not collectable, will be censored at date of relocation. Subjects who have died will be censored at the date of death. For subjects experiencing CRC recurrence, TTR will be calculated as the number of days from randomization until date of CT/MRI, or EoS date if the aforementioned date is missing, or recurrence date collected separately from sites if recurrence has not been entered into the eCRF (see Section 4.9 for details on data collection). For subjects not experiencing CRC recurrence, TTR will be calculated as the number of days from randomization until date of censoring (see above). The TTR event indicator will be defined as 1 for subjects who have experienced CRC recurrence with a CT/MRI/EoS/recurrence date within 3 years plus 21 days from randomization, and 0 for those that have not. The time variable will be named ttr3y, and the event indicator will be named rec status 3y.

TTR will also be assessed at 5 years (see Section 8.3). The variables *ttr5y* and *rec_status_5y* will be created similarly as described above, with censoring at 5 years plus 30 days.

For the secondary endpoint DFS assessed at 3 years, subjects who are free of CRC recurrence, second primary CRC, other cancer, or death from any cause will be censored at the date for which they are last known to be free of such events. Subjects who are free of the above events at 3 years plus 21 days (allowing for the 21-day visit-window) will be censored at that time-point. DFS will be calculated as the number of days from randomization until recurrence date (see definition in the above paragraph), EoS date, death date or date of other cancer collected separately from sites (see Section 4.9), or the date of censoring (see above). The DFS event indicator will be defined as 1 for subjects who have a DFS event within 3 years plus 21 days from randomization, where DFS events are defined as:

- Having EoS reasons CRC recurrence or death, or

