Primary endpoint	TTR assessed at 3 years between randomized arms	ttr3y	rec_status_3y	FAP	Mutation A
Secondary endpoint 1	DFS assessed at 3 years between randomized arms	dfs3y	dfs_status_3y	FAP	Mutation A
Secondary endpoint 2	TTR assessed at 3 years between randomized arms	ttr3y	rec_status_3y	FAP	Mutation B
Secondary endpoint 3	DFS assessed at 3 years between randomized arms	dfs3y	dfs_status_3y	FAP	Mutation B
Secondary endpoint 4	OS assessed at 5 years between randomized arms	os5y	os_status_5y	FAP	Mutation A
Secondary endpoint 5	OS assessed at 5 years between randomized arms	os5y	os_status_5y	FAP	Mutation B

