8.1 Primary efficacy analysis

The analysis of the primary endpoint TTR assessed at 3 years from randomization in subjects with somatic alterations in the PIK3CA gene (exons 9/20) will be performed on a subset of the FAP containing only subjects with such somatic alterations.

The primary efficacy analysis will consist of a Cox proportional hazards model (PHM), including the covariate *Treatment* (ASA vs Placebo, defined by randomization). The baseline hazard will be stratified by the covariates used in the randomization – location (colon/rectum), and stage (I/II/III, included as a categorical variable). The strata will thus be the following

- Stratum 1: Colon, Stage II
- Stratum 2: Colon, Stage III,
- Stratum 3: Rectum, Stage I,
- Stratum 4: Rectum, Stage II,
- Stratum 5: Rectum, Stage III.

The Breslow method will be used to handle tied event-times. The model is given by

$$h_i(t) = h_{0,i}(t) \cdot \exp(\beta_{Treat} \cdot Arm),$$

where $h_j(t)$ and $h_{0,j}(t)$ denote the hazard function and baseline hazard function, respectively, for stratum j, j=1,...,5, and Arm denotes randomized arm (ASA=1, Placebo=0).

A HR=exp(β_{Treat}) comparing the hazard rates of the ASA and placebo arms will be estimated, along with a two-sided 95 % CI, and a two-sided p-value for testing the null hypothesis

 H_0 : $\beta_{Treat} = 0$

against the alternative hypothesis

 H_1 : $\beta_{Treat} \neq 0$.

The proportional hazards assumption (PHA) of the Treatment variable will be assessed using the Grambsch-Therneau test with a significance level of 5 %. If the PHA is violated, the overall HR will still be reported as the primary efficacy estimate, but an additional analysis will be added where follow-up is divided into two intervals, 0-1.5 years, and 1.5-3 years from randomization, and one HR for Treatment will be estimated for each time interval by adding an interaction term between Treatment and the time intervals.

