In addition to the Cox PHM, TTR in the two treatment arms (ASA and Placebo) will be visually inspected by the cumulative incidence function (CIF) using Aalen-Johansen estimates, including 95% CIs, from time of randomization until three years of follow-up. Death will be considered a competing event. The 1- and 3-year Aalen-Johansen estimates of cumulative incidence of CRC recurrence in each arm, along with 95 % CIs, will also be presented. Kaplan-Meier (KM) curves estimating the net proportion of CRC recurrence, including 95% CIs, from time of randomization until three years of follow-up will be included as a supplementary figure.

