The statistical software R (R Foundation for Statistical Computing) will be used, in a version released less than a year before the time of analysis of the primary and secondary endpoints.

10 Listing of tables and figures

Note that the table and figure numbering in the below sections does not necessarily reflect the actual numbering in future publications. Some of the tables and figures may be published separately and in different order. Table formatting, e.g. number of decimals/significant digits, headings, row ordering etc. may be changed to follow the specifications of the selected journal(s).

Table 12. List of tables.

Table	Description	Population	Columns
Table 1.	Patient characteristics for randomized subjects in the ALASCCA trial.	FAP	Randomized to ASA Randomized to Placebo
Table 2.	Results from analysis of primary endpoint, and secondary endpoint 1-3. If the PHA is violated, one HR per time-interval (in addition to the overall HR).	FAP	N per randomized arm, no. of events per randomized arm, HR, 95% CI, p-value
Table 3.	Results from analysis of secondary endpoints 4-5.	FAP	N per randomized arm, no. of events per randomized arm, HR, 95% CI, p-value
Table 4.	Results from analyses of exploratory endpoints.	FAP/PP3	N per randomized arm, no. of events per randomized arm, HR, 95% CI
Table 5.	SAEs per randomized arm.	SP	Number of SAEs per randomized arm
Table 6.	AEs per randomized arm.	SP	Number of AEs per randomized arm
Supplementary Table 1.	Number of AEs per randomized arm and visit, stratified by type of AE.	SP	Number of AEs per randomized arm

Table 13. List of figures. Mutation A: Mutation in PIK3CA exons 9/20, Mutation B: Mutation in PIK3CA (other exons), PIK3R1, PTEN.

Figure	Description	Population	Axis labels (if applicable)
Figure 1.	CONSORT flowchart showing number of screened patients, exclusions, randomized subjects.		
Figure 2a.	CIF curves, with 95% CIs, comparing TTR assessed at 3 years between ASA and Placebo in subjects with somatic alterations in PIK3CA (exons 9/20).	FAP, Mutation A	X-axis "Months from randomization" Y-axis "Cumulative incidence of CRC recurrence (%)"
Figure 2b.	CIF curves, with 95% CIs, comparing TTR assessed at 3 years between ASA and Placebo in subjects with somatic alterations in PIK3CA (other exons), PIK3R1, or PTEN.	FAP, Mutation B	X-axis "Months from randomization" Y-axis "Cumulative incidence of CRC recurrence (%)"

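### Does it matter that SAP 8.1 reads the TTR curves at three years while the endpoint variable runs to 3 years plus 21 days?

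*SAP*

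**What the plan says.** SAP 6.2.1 builds the time variable ttr3y and its event indicator with the visit window included. Subjects "alive and free of CRC recurrence at 3 years plus 21 days (allowing for the 21-day visit-window) will be censored at that time-point". The event indicator is 1 for "CRC recurrence with a CT/MRI/EoS/recurrence date within 3 years plus 21 days from randomization". A recurrence is dated first by its CT or MRI. Table 9 assigns these variables to the primary endpoint, so the Cox hazard ratio and the event counts in Table 15 include the extra 21 days.

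SAP 8.1 then describes the cumulative incidence curves and the supplementary Kaplan-Meier curves as running "from time of randomization until three years of follow-up", and adds "The 1- and 3-year Aalen-Johansen estimates of cumulative incidence of CRC recurrence in each arm". It mentions neither the window nor a day number.

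Three other places bear on what 3 years means here. SAP 5.1 says that "all subjects will have at least 3 years of follow-up on August 9, 2024, allowing for the visit window of 21 days". Table 9 labels the ttr3y analysis "TTR assessed at 3 years between randomized arms". Table 13 describes the main figures as "CIF curves, with 95% CIs, comparing TTR assessed at 3 years between ASA and Placebo in subjects with somatic alterations".

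**The concern.** Scheduled scans fall at 1 and 3 years after randomization (SAP 4.1), at visits with a window of 21 days either side. Because a recurrence takes the date of its scan, recurrences can cluster around the third anniversary. That is why SAP 6.2.1 extends ttr3y.

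If the cumulative incidence is read at exactly 3 years (day 1096), a recurrence dated on days 1097 to 1117 enters the hazard ratio and the event count but not the absolute risk reported beside them. Two programmers could both follow the SAP and report different 3-year risks. The earlier read-out gives slightly lower risks in both arms and a slightly smaller difference between them. These are pre-specified results that accompany the primary analysis, so a mismatch deserves a check.

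**Working it through.** **Inputs.** Placebo 3-year risk 18%, RR 0.38, 150 per arm including 10% drop-out and 135 excluding it (SAP 4.5.2). The ASA risk is 0.18 × 0.38 = 6.84%.

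**The plan's own figure.** With the two-proportion test and pooled variance, the mean risk is (0.18 + 0.0684)/2 = 0.1242.

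n = [1.960 × √(2 × 0.1242 × 0.8758) + 0.842 × √(0.18 × 0.82 + 0.0684 × 0.9316)]² / (0.18 − 0.0684)² ≈ 136 per arm (stated: 135).

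Power at 135 is 79.7%. Adding drop-out gives 136/0.9 ≈ 152 (stated: 150). The planning risks are therefore a sound base, and the read-out day enters none of this.

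**What 3 years means in SAP 5.1.** The last subject was randomized on 19 July 2021. Three years later is 19 July 2024, and 21 more days is 9 August 2024, the date on which SAP 5.1 says all subjects have at least 3 years of follow-up with the window allowed for. So the SAP uses nearly the phrase of 8.1 in a sense that includes the 21 days.

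**Gap under a constant hazard.** Let D = 3 × 365.25 = 1095.75 days. The risk at D + 21 is 1 − (1 − p)^((D+21)/D), with exponent 1116.75/1095.75 = 1.01916.

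- Placebo: 1 − 0.82^1.01916 = 18.31%, a gap of 0.31 points or 0.47 events per 150.
- ASA: 1 − 0.9316^1.01916 = 6.97%, a gap of 0.13 points or 0.19 events per 150.
- Standard error of an 18% estimate with 150 subjects: √(0.18 × 0.82/150) = 3.1 points.

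**Gap if events cluster at scans.** This simulation of 2,000,000 subjects per arm uses the Aalen-Johansen estimator. It assumes 5% competing death by 3 years and scans uniform over ±21 days. The share of recurrences found only at scheduled scans is also assumed; the documents give none of these three.

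| Scan-only share | Placebo, day 1096 / 1117 | ASA, day 1096 / 1117 | Arm difference, day 1096 / 1117 |
|---|---|---|---|
| 0% | 17.6 / 17.9% | 6.7 / 6.8% | 10.9 / 11.1 points |
| 20% | 16.4 / 17.8% | 6.2 / 6.7% | 10.2 / 11.0 points |
| 50% | 14.7 / 17.6% | 5.6 / 6.7% | 9.1 / 10.9 points |

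The ratio of the two risks stays between 0.378 and 0.382 throughout. If every scan falls on or before the anniversary, the placebo gap is only 0.15 to 0.3 points.

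A cruder bound assumes that 5 to 30% of recurrences are found at the year-3 scan and that 25 to 75% of those scans are late. An 18% placebo figure would then read between 18 × (1 − 0.05 × 0.25) = 17.8% and 18 × (1 − 0.30 × 0.75) = 13.95%.

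**Cost of reading at day 1117.** SAP 6.2.1 also censors at the date last known free of recurrence. If subjects with a clean in-window scan are censored at that scan, the risk set thins before day 1117 and late events carry too much weight. In the same placebo setting, with 50% of subjects so censored, the day-1117 estimate is 18.6% (20% scan-only) or 19.6% (50% scan-only). With 80% so censored it is about 19.8% or 22.6%. With none so censored it is about 17.7% or 17.5%. The censored share is again an assumption.

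**The case for a change.** The best case for acting is that the SAP extended ttr3y precisely because scans cluster around the anniversary, and a default time of 36 months in the code would undo that for the absolute risks. The shift is systematic, in the same direction in both arms, and one sentence would prevent it. The worst assumed case, about 4 points in placebo, exceeds one standard error.

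Part of this stands. Section 8.1 names no day, and the two readings can give different figures. What does not follow is that one of them is wrong. An Aalen-Johansen estimate read at exactly 3 years correctly estimates recurrence detected by 3 years; it is low only if the target is taken to be 3 years plus 21 days.

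The large gaps need many scan-only recurrences together with many late scans. Protocol 10.4 describes the standard programme as timed from surgery, which would put such scans before the anniversary, where the gap is smallest; SAP 4.1 times them from randomization.

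Moving only the 3-year read-out would also leave the 1-year estimate in the same sentence on another convention, although its scan has the same window. The later day brings its own risk from thinning. The rule that censors confirmed recurrence-free subjects at 3 years plus 21 days, and the chart review in SAP 4.9.4, should limit that thinning, but the documents do not show by how much.

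**Conclusion.** No change to the plan is needed. The gap is a missing detail that an analyst can settle sensibly: pick the day, label the estimate, and note that the hazard ratio and event counts run to 3 years plus 21 days. The SAP's other usage leans toward the ttr3y horizon, since 8.1 itself opens with "The analysis of the primary endpoint TTR assessed at 3 years from randomization" and Table 9 ties that endpoint to ttr3y. The figure templates are not visible in the available text, so their axis limits cannot decide the matter.

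Followed either way, the plan gives a sound result. The hazard ratio, its confidence interval, the p-value and the sample size do not depend on the read-out day. The difference supported by the plan's own planning risks, under a constant hazard, is about 0.3 points in placebo and 0.1 in ASA. Larger differences rest on assumed scan-detected shares and scan timing.

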8.2 Secondary efficacy analyses

8.2.1 Secondary endpoints 1-5

The secondary endpoints 1-5 will be analyzed as described in Section 8.1. DFS and OS will be visualized using Kaplan-Meier estimates. For OS endpoints, the KM estimates for the net proportion or survival will be made at 5 years, and any analyses of OS endpoints will be performed earliest in 2026 when each randomized subject has a full 5-year follow-up. See Table 9 for specifications on endpoint variables, event indicators and subsets for secondary endpoints 1-5.

8.2.2 Safety and tolerability

SAEs and AEs in the SP will be listed and summarized, stratified by randomized arm. All SAEs will be coded by authorized study personnel according to the most recent version of MedDRA. SAEs and AEs will be reported in EudraCT and clinicaltrials.gov.

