#### 10.2.4 Treatment visits (Visit 5, 7, 9, 11, 13, 15)

The patient will visit the site every 6 months. A visit window of  $\pm 21$  days is allowed. Follow-up is otherwise according to standard national guidelines.

---

The following assessments will be performed during the treatment visits;

- Assess AEs
- Record concomitant medication
- Compliance and drug accountability check
- Provide the patient with IMP for 6 months + 1 week (not applicable for visit 15)

In addition to the items that will be performed during the treatments visits, the following will be performed at the time of visit 7 and 15 (after 1 and 3 years);

- CT/MRI (Magnetic Resonance Imaging) thorax and abdomen
- CEA (Optional)

In case of any recurrence the patient will be taken care of according to standard treatment at the site and will be withdrawn from further study treatment.

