#### Exception

Events directly connected to expected chemotherapeutics side effects e.g. nausea, diarrhoea neutropenia and infections related to neutropenia will not be reported as AEs.

Planned enterostomy closure performed after administration of IMP and complications after the closure will not be reported as AE/SAE.

In case of any bleeding events related to the above, the event should be reported as an AE/SAE.

The following evaluations are to be done by the Investigator in connection with the AE:

- *description of the AE*
  - If possible the Investigator uses the diagnosis for description of the event. If not the diagnosis is decided, report the primary sign or symptom as the AE or SAE term
- *seriousness*
  - Yes or No, see definition of a SAE for seriousness, as of above.
- *intensity*
  - Mild - Symptoms which are easily tolerated (acceptable)

- Moderate - Symptoms which interfere with usual activity (disturbing)
- Severe - Symptoms which give incapacity to do usual activity (unacceptable)

If the intensity changes during the period of the AE the maximum intensity should be recorded.

- *duration of the AE (start - end)*
- *action taken due to the AE*
  - None
  - IMP stopped
- *causality rating with investigational medicinal product*
  - Not related: Indicates that the AE is definitely not related to the study drug.
  - Related: .
    - The AE could have been produced by the patient's clinical status or the medicinal product.
    - The AE follows a reasonable temporal sequence from the time of administration of the medicinal product, and can not be reasonably explained by the known characteristics of the patient's clinical status.
- *outcome of the AE*
  - Recovered/Resolved
  - Recovering/Resolving
  - Not recovered/Not resolved
  - Recovered/Resolved with sequelae
  - Fatal
  - Unknown

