#### 10.13.7 Determination of sample size

Power was set to 80%, total follow-up to 36 months and significance level to 0.05 (two-sided). The 36 months recurrence rate in the placebo arm was estimated to 18% based on the Stage/RF-specific estimates in Osterman and Glimelius (ref\*). With the assumptions of 10%

loss to follow-up and a sample size of 150 patients in each arm, a reduction of 62% (RR=0.38) in the 36 months recurrence rate can be detected.

\*Recurrence Risk After Up-to-Date Colon Cancer Staging, Surgery, and Pathology: Analysis of the Entire Swedish Population. Osterman E, Glimelius B. *Dis Colon Rectum*. 2018 Sep;61(9):1016-1025.

If 15% of the patients screened have hotspot mutations (exon 9 and 20) in *PI3KCA* a total of 3750 patients will needed to be screened. This also includes approximately 15% of the patients that will be excluded due to tumor stage 1. In protocol version 5.2, the number of patients is changed after pilots and first 1000 patients have been included when better estimation on drop-out and mutation rate in *PIK3CA* was available.

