4.5.2 Updated calculation in protocol version 5.2

An updated sample size calculation was included in the ALASCCA Clinical Study Protocol Version 5.2 after 3206 patients had been screened. The three-year cumulative incidence of recurrence in the placebo arm was estimated to 18 % based on the Stage/Risk factor-specific estimates in Osterman and Glimelius (2018)^[1], and a 10 % drop-out rate was assumed. A total of 150 subjects in each arm would have to be included to detect a risk ratio (RR) of 0.38 for comparison between the ASA and placebo arms with 80 % power and a two-sided alpha of 0.05. Assuming 15 % of screened patients have somatic alterations in the PIK3CA (exon 9 and/or 20) gene, a total of 3750 patients will have to be screened. The estimate of a 15 % mutation rate was based on the 3206 first screened patients. The sample size calculation was based on a two-sample test for proportions. Details of the initial sample size calculation are listed in Table 2.

Table 2. Details of the updated sample size calculation in protocol version 5.2.

Power (%)	80
Two-sided alpha (%)	5
Minimal follow-up (months)	36
Mutation rate (%)	15
3-year cumulative incidence of recurrence in the placebo arm (%)	18
RR	0.38
Number of subjects in each arm (incl. 10 % drop-out)	150
Number of subjects in each arm (excl. 10 % drop-out)	135
Number of patients needed to be screened	3750

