7.2 Safety interim analysis 2020

Data was extracted from the eCRF on January 17th, 2020, including subjects that were randomized up to and including October 21st, 2019, with follow-up up to and including January 17th, 2020. The safety report was sent to the SMC on March 5th, 2020.

The number of SAEs were summarized by randomized arm and visit. Fisher's exact test was used to test differences in frequencies of SAEs between randomized arms for each visit. Information on all SAEs were listed, see Table 8 for details. Similarly, the total number of AEs, and number of AEs per AE type (using the categories listed under "Type of SAE" in Table 8), were summarized by randomized arm and visit, and compared between arms for each visit using Fisher's exact test. The number of subjects with multiple AEs was also summarized by randomized arm, visit, and type of AE.

Table 8. SAE and AE details included in the 2018 and 2020 safety reports to the SMC

SAE variable	Categories
Visit number	4-9 (2018 report), 4-15 (2020 report)
SAE day	Day in relation to randomization date
Randomized arm	0/1 (not disclosing associated treatment)
Type of SAE	 Hematological
	 Cancer
	 Cardiovascular
	 CNS/Neurological
	 Dermatological
	- Endocrine
	 Eyes, ears, nose, throat
	 Gastrointestinal
	Urogenital
	Hormonal
	Immunological
	 Musculoskeletal
	Respiratory
	– Other
SAE description	 Leads to death
	 Is life threatening
	Other important medical event
	 Requires hospitalization for more than 24
	hours or extended medical care
	Causes permanent or significant
	invalidity/functional impairment
Intensity	– Mild
	- Moderate
T (185)	- Severe
Treatment modification	- Unchanged
	- Stopped
B "	Other, e.g., treatment pause
Result	- Restored
	- Under improvement
	Not Restored, with sequels
	Death

8 Analysis of trial endpoints

All tests and confidence intervals (CIs) will be two-sided. The significance level will be 5 %, and CIs will have 95 % confidence level. The endpoints and their respective variables and populations are summarized in Table 9.

Table 9. Specification of variables and populations for the primary endpoint or secondary endpoints 1-5 in the ALASCCA trial. Mutation A: PIK3CA exon 9 and 20 hotspot small mutations, Mutation B: other PIK3CA, PIK3R1 and PTEN non-silent small mutations and focal/homozygous deletion of PTEN.

Endpoint	Specification	Time variable	Event indicator	Population	Subgroup

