Adjuvant chemotherapy in colon	Fluorouracil/capecitabin						
cancer	Fluorouracil/capecitabin + oxaliplatin						
	Other adjuvant chemotherapy						
	No adjuvant chemotherapy						
	Missing						
Adjuvant chemotherapy in rectal	Fluorouracil/capecitabin						
cancer	Fluorouracil/capecitabin + oxaliplatin						
	Other adjuvant chemotherapy						
	No adjuvant chemotherapy						
	Missing						

¹V600E ²Exons 12, 13, 59, 61, 117 and/or 146

Table 15. Table template for Table 2: Results from analysis of primary endpoint, and secondary endpoint 1-3. If the PHA is violated, one HR per time-interval (in addition to the overall HR).

Outcome	N (n events) in ASA arm	N (n events) in Placebo arm	HR ASA vs Placebo (95% CI; p)
TTR in PIK3CA exons 9/20			
DFS in PIK3CA exons 9/20			
TTR in PIK3CA (other exons), PIK3R1, PTEN			
DFS in PIK3CA (other exons), PIK3R1, PTEN			

Table 16. Table template for Table 3: Results from analysis of secondary endpoints 4-5.

Outcome	N (n events) in ASA arm	N (n events) in Placebo arm	HR ASA vs Placebo (95% CI; p)
OS in PIK3CA exons 9/20			
OS in PIK3CA (other exons), PIK3R1, PTEN			

Table 17. Table template for Table 4: Results from analysis of exploratory endpoints.

Outcome	Subgroup	N (n events) in ASA arm	N (n events) in Placebo arm	HR ASA vs Placebo (95% CI)
TTR	PIK3CA exons 9/20 (PP3 population)			
TTR	PIK3CA (other exons), PIK3R1, PTEN (PP3 population)			

Table 18. Table template for Table 5: Number of SAEs per randomized arm.

		Randomiz	ed to ASA	Randomized	to Placebo
		Number of SAEs (%)	N subjects in SP	Number of SAEs (%)	N subjects in SP
Total					
Time from randomization (months)	Median (IQR, min- max)				
Type of SAE	Hematological				
• •	Cancer				
	Cardiovascular				
	CNS/Neurological				
	Dermatological				
İ	Endocrine				

		Randomize	Randomized to ASA		to Placebo
		Number of SAEs (%)	N subjects in SP	Number of SAEs (%)	N subjects in SP
	Eyes, ears, nose, throat				
	Gastrointestinal				
	Urogenital				
	Immunological				
	Musculoskeletal				
	Respiratory				
	Other				
SAE description	Leads to death				
	Is life threatening				
	Other important				
	medical event				
	Requires				
	hospitalization for more than 24 hours or				
	extended medical care				
	Causes permanent or significant invalidity/functional				
	impairment				
Intensity	Mild				
•	Moderate				
	Severe				
Treatment modification	Unchanged				
	Stopped				
	Other, e.g. treatment				
	pause				
Result	Restored				
	Under improvement				

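### SAP Tables 18 and 19 pool colorectal cancer recurrences and deaths with other adverse events, so if ASA works the pooled rows could dilute or reverse an excess of other harms

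*SAP*

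**What the plan says.** **Definitions.** Protocol 10.8.7.1 defines an AE as any untoward occurrence, related to treatment or not. It makes an AE serious if, among other criteria, it causes death, threatens life or requires hospital care. Protocol 10.8.7.2 requires all AEs to be recorded.

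**Exceptions.** The first is: "Events directly connected to expected chemotherapeutics side effects e.g. nausea, diarrhoea neutropenia and infections related to neutropenia will not be reported as AEs". The others are planned enterostomy closure with its complications, pre-existing conditions that do not worsen, and procedures planned before the first dose (10.8.7.2 and 10.8.7.3). CRC recurrence, progression and CRC death are not listed. SAP 4.3 makes recurrence and CRC death the events of the primary endpoint, time to recurrence.

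**Treatment after recurrence.** Under protocol 10.2.4 a patient with recurrence "will be withdrawn from further study treatment". SAP 4.8 lists CRC recurrence among the end-of-study reasons.

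**Display.** SAP 8.2.2 states that "SAEs and AEs in the SP will be listed and summarized, stratified by randomized arm". The templates in SAP 10.1 count events by arm, with Groups A and B together. Table 18 (SAEs) and Table 19 (AEs) both have a Total, event-type rows including Cancer, intensity, treatment modification (with a Stopped row) and result (with a Death row). Table 18 also has the row "Leads to death". Apart from the type rows, none is split by cause.

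**The concern.** Safety and tolerability is secondary objective 6 in SAP 4.2.2. The rows read first for it are the total, the fatal events and the events that stopped treatment. If recurrences enter those rows and ASA lowers recurrence, the placebo arm gains events that are efficacy outcomes. In the pooled rows these would offset an excess of bleeding or other harm on ASA, so the tolerability comparison would improve because the primary endpoint did.

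The type rows undo this only in part. A reader can subtract Cancer from the Total, but not from the fatal, intensity, Stopped or result rows. The Cancer row also does not separate recurrence of the study cancer from a new primary.

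**Working it through.** **1. The planning figure used for scale.** SAP 4.5.2 reads "The three-year cumulative incidence of recurrence in the placebo arm was estimated to 18" percent, and "A total of 150 subjects in each arm would have to be included to detect a risk ratio (RR) of 0.38", with 80% power, two-sided alpha 0.05 and a two-sample test for proportions. The ASA risk is 0.18 × 0.38 = 0.0684 and the mean risk is 0.1242.

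n = [1.96 × √(2 × 0.1242 × 0.8758) + 0.842 × √(0.18 × 0.82 + 0.0684 × 0.9316)]² / 0.1116² ≈ 136 per arm

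The SAP gives 135 before drop-out, where power is 79.7%. Then 136 / 0.9 gives 152 with drop-out, against 150. The planning figure is reproduced closely and is used below only for scale.

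**2. Expected recurrences over 3 years.** The safety tables pool both mutation groups, so the arm size is 300 (protocol 10.7.3: 150 from each group). Applying 18% to Group B as well is an assumption, because the documents give that figure for Group A.

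| | Placebo | ASA | Fewer on ASA |
|---|---|---|---|
| Group A, 150 per arm | 150 × 0.18 = 27.0 | 150 × 0.0684 = 10.3 | 16.7 |
| A+B, no effect in B | 54.0 | 10.3 + 27.0 = 37.3 | 16.7 |
| A+B, same effect in B | 54.0 | 20.5 | 33.5 |

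Counting only the 135 per arm left after drop-out, Group A gives 24.3 v 9.2, a difference of about 15.

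**3. Share reported as SAEs.** The documents do not give this share, so a range is shown, with each recurrence counted once.

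| Assumed share | Offset, no effect in B | Offset, same effect in B |
|---|---|---|
| 25% | 4.2 | 8.4 |
| 50% | 8.4 | 16.7 |
| 100% | 16.7 | 33.5 |

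**4. Comparison with the protocol's own bleeding rates.** Protocol 10.5 gives about 0.1% per year for extra gastrointestinal bleeding and about 0.01% for intracranial haemorrhage (no time unit stated; per year is assumed here).

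300 × 3 × 0.001 + 300 × 3 × 0.0001 = 0.9 + 0.09 ≈ 1.0 extra event on ASA

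Other events being equal, the expected ASA-minus-placebo difference in the total is +1.0 with CRC events removed. With all recurrences reported it is 1.0 − 16.7 ≈ −15.8 (unrounded inputs) to 1.0 − 33.5 = −32.5. At a 25% share it is about −3.2 to −7.4.

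**5. Illustration for a larger harm.** Assume a placebo risk b of a non-CRC SAE, a true harm ratio of 1.5 on ASA, a reported share s, and independence. With recurrence risk r in the arm, the risk of any SAE is b + (1 − b) × r × s on placebo; on ASA, b is replaced by 1.5b. For b = 10%, s = 50% and no effect in B (pooled ASA recurrence risk 37.3 / 300 = 0.1242):

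- placebo: 0.10 + 0.90 × 0.18 × 0.5 = 0.181
- ASA: 0.15 + 0.85 × 0.1242 × 0.5 = 0.203
- ratio: 1.12, against a true 1.5

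| b | Effect in B | s = 25% | s = 50% | s = 100% |
|---|---|---|---|---|
| 10% | none | 1.26 | 1.12 | 0.98 |
| 10% | same as A | 1.17 | 0.99 | 0.79 |
| 20% | none | 1.36 | 1.26 | 1.12 |
| 20% | same as A | 1.32 | 1.19 | 1.01 |

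The ratio is diluted in every cell and falls below 1 in three of the twelve.

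**The case against.** A reader might infer that the tables would hide an ASA harm. The documents do not support that. Both templates have separate gastrointestinal, CNS/neurological, hematological and cardiovascular rows. Events are listed individually (SAP 8.2.2), and protocol 10.13.4 plans preferred terms within System Organ Class. With about one extra bleed expected, the total is not where bleeding would be found in any case. All of this stands. What it leaves open is the pooled rows: neither template has a bleeding row, and listings do not correct a summary by arm.

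It is also fair that neither document tells sites to report recurrence as an SAE. A scan-detected recurrence is serious only if it meets a criterion, and recurrence has its own end-of-study reason and endpoint fields. The mixture is therefore permitted by the rules as written, but its extent is unknown. A non-serious recurrence still fits the AE definition and can enter Table 19.

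Two rows need particular care:

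- **Stopped.** One might assume that every recurrence lands here. Some are found at Visit 15, when treatment ends anyway, or in patients already off treatment, so the figures are upper bounds for this row.
- **Fatal SAEs.** Recurrence ends the treatment part, and SAP Table 4 shows AE assessment only through Visit 15, while protocol 10.8.7.2 mentions AE collection in follow-up. Many CRC deaths may never reach Table 18, so this part is the least certain.

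Finally, one might read the interim reports as having compared overall SAE totals. SAP 7.2 says Fisher's exact test "was used to test differences in frequencies of SAEs between randomized arms for each visit", not on a total, and in the 2018 report the test was applied to AEs. Those reports are complete, and nothing here turns on them.

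**Conclusion.** The point holds as a matter of presentation. Followed as written, the plan lets primary-endpoint events enter the by-arm safety summary and does not separate them in the pooled rows. If ASA works, the bias in those rows favours ASA.

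At the planned effect the offset is at most about 17 events (no effect in Group B) or about 33 (same effect there), and about 4 to 8 if a quarter of recurrences are reported as SAEs. This rests on an 18% placebo risk in both groups, no loss to follow-up and one SAE per recurrence. Because the tables count events, a recurrence with several admissions could count more than once. Even the smallest of these offsets exceeds the roughly one extra bleed implied by protocol 10.5. The finding is dilution or possible reversal in pooled rows, not concealment of bleeding. It merits a change because the change is cheap.

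**What to change.** Before unblinding, amend SAP 8.2.2 and Tables 18 and 19 as follows:

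- Show the Total, intensity, treatment-modification and result rows, and the fatal-SAE row of Table 18, in two forms: all events, and excluding CRC recurrence or progression and CRC death.
- Identify the excluded events from the end-of-study reason, the recurrence data and the recorded cause of death.
- Give CRC recurrence its own type row, separate from new primary cancers.

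The all-events figures stay, so nothing is lost. The completed interim reports need no change.

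The cost is extra rows or columns and some blinded attribution work. An SAE such as bowel obstruction may need case review to decide whether it belongs to a recurrence. Cause of death is to be recorded under protocol 10.8.4, but SAP Table 5 lists only death and its date, so its source should be named.
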